9.4.1 Primary endpoints

The primary endpoint for both phases will be analyzed using a natural logarithm transformation consistent with sample size assessments in Section 9.2 given a distribution for the endpoint which is skewed right. Further, the percent change endpoint is a re-scaled fold change from baseline statistic for which such a transformation is often conducted. The mean fold change and percent change estimates are interpretable as geometric means given the logarithmic transformation.

Page: 60 of 86

9.4.1.1 Lead-in Phase

The patient testosterone levels at baseline and week 12 in the evaluable population will be transformed to natural logarithm values. The mean and 95% confidence interval of the differences between week 12 and baseline values will be computed and back transformed by exponentiation to obtain the mean fold change M_F with its 95% confidence interval [L_F , U_F]. The mean percent change Δ can be obtained as $\Delta = 100*(M_F-1)$ with confidence interval [$100*(L_F-1)$, $100*(U_F-1)$]. In addition to the estimated mean percent change and its confidence interval, summary statistics will include the mean fold change with confidence intervals, and the range, minimum, maximum and quartiles of percent change computed from the raw week 12 and baseline testosterone values.

9.4.1.2 Randomized Phase

The patient level differences between natural log transformed testosterone values at week 12 and baseline will be computed. These differences will be compared across the darolutamide and enzalutamide arms using a two-sample t-test. Two-sided p-values from this t-test will be reported to assess whether the null hypothesis can be rejected in favor of the alternate hypothesis in Section 9.1. Additionally, the estimated difference between darolutamide and enzalutamide and the 95% confidence limits from the t-test will be back transformed by exponentiation to obtain the ratio of the fold change in testosterone values from baseline for darolutamide, to that for enzalutamide and the confidence limits for this estimate. Within treatment group mean percent change and confidence intervals as well as other summary statistics described for the lead-in phase will also be reported.

9.4.2 Secondary Endpoints

All secondary endpoints will be analyzed in the evaluable population with the exception of the AEs, which will be analyzed in the safety population.

9.4.2.1 Lead-in Phase

For testosterone at the visits at week 24 and 52, the differences between the log transformed data at the visit and that at baseline will be estimated with 95% confidence intervals using SAS PROC MIXED with the ESTIMATE statement and a Toeplitz covariance structure.

These are to be transformed to mean percent change and 95% confidence intervals using the same steps as for the primary analysis in the lead-in phase. Results will be summarized in a similar manner to the primary endpoint for testosterone at week 24 and 52. PSA response rates will be summarized at week 4, 12, 24, 36 and 52 using frequencies and percentages. Response levels to be summarized will be 30%, 50% and 90% decreases.

Feminizing side effects of gynecomastia, breast tenderness/pain, nipple pain, and hot flush will be summarized using frequencies and percentages.

9.4.2.2 Randomized Phase

For testosterone at the visits at week 24 and 52, and for each of the sex hormones, and for each of the components of fat and glucose metabolism at weeks 4, 12, 24 and 52, the differences between the log transformed data at the visit and that at baseline will be compared across treatment groups with 95% Confidence Intervals using SAS PROC MIXED with the SLICE option and a Toeplitz covariance structure. These are to be transformed to the ratio of the fold change from baseline for darolutamide to that for enzalutamide and 95% confidence intervals using the same steps as for the primary analysis in the randomized phase. Results will be analyzed in a similar manner to the primary endpoint for testosterone at week 24 and 52 and for the other sex hormones and the metabolic endpoints. These analyses will be summarized graphically using the mean percent change over time with 95% confidence intervals at each visit by treatment group, flagging visits where differences are significant at the nominal 0.05 and 0.01 levels.

Page: 61 of 86

PSA response rates will be compared descriptively across treatments at week 4, 12, 24, 36 and 52 using frequencies and percentages. Response levels to be summarized will be 30%, 50% and 90% decreases.

Differences in the FACT-P prostate cancer subscale will be summarized at each visit using PROC Mixed with the SLICE option and the mean subscale score will be depicted graphically over time with 95% confidence intervals at each visit by treatment group, flagging visits where differences are significant at the nominal 0.05 and 0.01 levels.

Feminizing side effects of gynecomastia, breast tenderness/pain, nipple pain, and hot flush will be summarized using frequencies and percentages by treatment group.

9.4.3 Other Pre-Specified Endpoints

Details on the analyses of exploratory endpoints, including markers of bone turnover and physical function, will be described in the statistical analysis plan.

9.4.4 Safety Analyses

All safety analyses will be descriptive and will be performed on the safety population. Safety data will be summarized descriptively for the lead-in phase and by treatment group for the randomized phase.

All AEs will be coded using the latest version prior to data base lock of the Medical Dictionary for Regulatory Activities (MedDRA).

Further details on safety analyses will be described in the SAP.

NOTE: AEs and safety lab parameters will be presented with their worst NCI-CTCAE grade.

9.5 Interim Analyses

No interim analysis is planned.

9.6 Data Monitoring Committee (DMC)

No data monitoring committee, dose escalation committee, or similar review group will be used for this study.

10. Appendices

10.1 Appendix 1: Study Governance Considerations

10.1.1 Regulatory and Ethical Considerations

This study will be conducted in accordance with the protocol and with the following:

- Consensus ethical principles derived from international guidelines including the Declaration of Helsinki and Council for International Organizations of Medical Sciences (CIOMS) International Ethical Guidelines
- Applicable ICH Good Clinical Practice (GCP) Guidelines
- Applicable laws and regulations

The protocol, protocol amendments, ICF, Investigator Brochure, and other relevant documents (e.g., advertisements) must be submitted to an IRB/IEC by the investigator and reviewed and approved by the IRB/IEC before the study is initiated.

Any amendments to the protocol will require approval by IRB/IEC as well as by regulatory authorities (as applicable) before implementation of changes made to the study design, except for changes necessary to eliminate an immediate hazard to study participants.

The investigator will be responsible for the following:

Page: 62 of 86

- Providing written summaries of the status of the study to the IRB/IEC annually or more frequently in accordance with the requirements, policies, and procedures established by the IRB/IEC.
- Notifying the IRB/IEC of SAEs or other significant safety findings as required by IRB/IEC procedures.
- Providing oversight of the conduct of the study at the site and adherence to requirements of ICH guidelines, the IRB/IEC, and all other applicable local regulations.

10.1.2 Financial Disclosure

Investigators and sub-investigators will provide the Sponsor with sufficient, accurate financial information as requested to allow the Sponsor to submit complete and accurate financial certification or disclosure statements to the appropriate regulatory authorities. Investigators are responsible for providing information on financial interests during the course of the study and for 1 year after completion of the study.

10.1.3 Informed Consent Process

- The investigator or his representative will explain the nature of the study to the participant or his legally authorized representative* (if acceptable by local law) and answer all questions regarding the study.
- Participants must be informed that their participation is voluntary. Participants or their legally authorized representative* will be required to sign a statement of informed consent that meets the requirements of 21 CFR 50, local regulations, ICH guidelines, Health Insurance Portability and Accountability Act (HIPAA) requirements, where applicable, and the IRB/IEC or study center.
- The medical record must include a statement that written informed consent was obtained before the participant was enrolled in the study and the date the written consent was obtained. The authorized person obtaining the informed consent must also sign the ICF.
- Participants must be re-consented to the most current version of the ICF(s) in a timely manner if new information becomes available that may be relevant to the participant's willingness to continue participation in the trial.
- A copy of the ICF(s) must be provided to the participant or the participant's legally authorized representative*.
 - *Participants who are rescreened are required to sign a new ICF.

10.1.4 Data Protection

- Participants will be assigned a unique identifier by the Sponsor. Any participant records
 or datasets that are transferred to the Sponsor will contain the identifier only; participant
 names or any information which would make the participant identifiable will not be
 transferred.
- The participant must be informed that his personal study-related data will be used by the Sponsor in accordance with local data protection law. The level of disclosure must also be explained to the participant.
- The participant must be informed that his medical records may be examined by Clinical Quality Assurance auditors or other authorized personnel appointed by the Sponsor, by appropriate IRB/IEC members, and by inspectors from regulatory authorities.

10.1.5 Publication Policy

• The results of this study may be published or presented at scientific meetings. If this is foreseen, the investigator agrees to submit all manuscripts or abstracts to the Sponsor before submission. This allows the Sponsor to protect proprietary information and to provide comments.

Page: 63 of 86

- The Sponsor will comply with the requirements for publication of study results. In accordance with standard editorial and ethical practice, the Sponsor will generally support publication of multicenter studies only in their entirety and not as individual site data. In this case, a coordinating investigator will be designated by mutual agreement.
- Authorship will be determined by mutual agreement and in line with International Committee of Medical Journal Editors authorship requirements.

10.1.6 Dissemination of Clinical Study Data

Result summaries of Bayer's sponsored clinical trials in drug development Phases 2, 3 and 4 and Phase 1 studies in patients are provided in the Bayer Trial Finder application after marketing authorization approval, in line with the position of the global pharmaceutical industry associations laid down in the "Joint Position on the Disclosure of Clinical Trial Information via Clinical Trial Registries and Databases". In addition, results of clinical drug trials will be provided on the publicly funded websites www.ClinicalTrials.gov (US National Library of Medicine) and www.clinicaltrialsregister.eu (the European clinical trials information system, CTIS) in line with the applicable regulations.

Bayer commits to sharing upon request from qualified scientific and medical researchers patient-level clinical trial data, study-level clinical trial data, and protocols from clinical trials in participants for medicines and indications approved in the United States (US) and European Union (EU) on or after 01 JAN 2014 as necessary for conducting legitimate research.

All Bayer-sponsored clinical trials are considered for publication in the scientific literature irrespective of whether the results of the clinical trials are positive or negative.

10.1.7 Data Quality Assurance

- All participant data relating to the study will be recorded on printed or electronic CRF unless transmitted to the Sponsor or designee electronically (e.g., laboratory data). The investigator is responsible for verifying that data entries are accurate and correct by physically or electronically signing the CRF.
- The investigator must maintain accurate documentation (source data) that supports the information entered in the CRF.
- The investigator must permit study-related monitoring, audits, IRB/IEC review, and regulatory agency inspections and provide direct access to source data documents.
- The Sponsor or designee is responsible for the data management of this study including quality checking of the data.
- Study monitors may perform ongoing source data verification to confirm that data entered into the CRF by authorized site personnel are accurate, complete, and verifiable from source documents. They will review source data to ensure that the safety and rights of participants are being protected that the safety and rights of participants are being protected and that the study is being conducted in accordance with the currently approved protocol and any other study agreements, ICH good clinical practice (GCP), and all applicable regulatory requirements.
- Records and documents, including signed ICFs, pertaining to the conduct of this study
 must be retained by the investigator after study completion for the retention period as
 set forth in the Investigator Agreement unless local regulations or institutional policies
 require a longer retention period. No records may be destroyed during the retention
 period without the written approval of the Sponsor. No records may be transferred to
 another location or party without written notification to the Sponsor.

10.1.8 Source Documents

• Source documents provide evidence for the existence of the participant and substantiate the integrity of the data collected. Source documents are filed at the investigator's site.

Page: 64 of 86

- Data reported on the CRF or entered in the eCRF that are transcribed from source documents must be consistent with the source documents or the discrepancies must be explained. The investigator may need to request previous medical records or transfer records, depending on the study. Also, current medical records must be available.
- Definition of what constitutes source data can be found in the Source Data Location
 List

10.1.9 Study and Site Closure

The Sponsor reserves the right to close the study site or terminate the study or individual sections of this study (e.g., treatment arms, dose cohorts, centers) at any time for any reason at the sole discretion of the Sponsor. Study sites will be closed upon study completion. A study site is considered closed when all required documents and study supplies have been collected and a study-site closure visit has been performed.

The investigator may initiate study-site closure at any time, provided there is reasonable cause and sufficient notice is given in advance of the intended termination.

Reasons for the early closure of a study site by the Sponsor or investigator may include but are not limited to:

- Failure of the investigator to comply with the protocol, the requirements of the IRB/IEC or local health authorities, the Sponsor's procedures, or GCP guidelines;
- Inadequate recruitment of participants by the investigator;
- Discontinuation of further study treatment development;
- If the study is prematurely terminated or suspended, the Sponsor shall promptly inform the Investigators, the IECs/IRBs, the regulatory authorities, and any contract research organization(s) used in the study of the reason for termination or suspension, as specified by the applicable regulatory requirements. The Investigator shall promptly inform the participant and should assure appropriate therapy and/or follow-up.
- If the risk-benefit ratio becomes unacceptable owing to, for example:
 - o Safety findings from this study (e.g., SAEs);
 - o Results of parallel clinical Bayer studies or emerging data from literature;
 - o Results of parallel animal studies (on e.g., toxicity, teratogenicity, carcinogenicity or reproduction toxicity).
- If the study conduct (e.g., recruitment rate; dropout rate; protocol compliance) does not suggest a proper completion of the trial within a reasonable period.
- Strategic reasons (e.g., the clinical development of the drug is stopped).
- The site is entitled to end its participation in the study if necessary due to medical or ethical reasons.

For any of the above closures, the following applies:

- Closures should occur only after consultation between involved parties. Final decision on the closure must be in writing.
- All affected institutions (e.g., IEC(s)/IRB(s); regulatory authority(ies); study center; head of study center) must be informed as applicable according to local law.
- All study materials (except documentation that must remain stored at site) must be returned to the Sponsor. The investigator will retain all other documents until

Page: 65 of 86

notification is given by the Sponsor for destruction.

• In the event of a study closure, participants on treatment and those in post-study followup, must be taken care of in an ethical manner.

Details for individual participant's withdrawal can be found in Section 7.

10.2 Appendix 2: Clinical Laboratory Tests

- The tests detailed in Table 1–1 will be performed by the local laboratory.
- Protocol-specific requirements for inclusion or exclusion of participants are detailed in Section 5.1 and Section 5.2 of the protocol.
- Additional tests may be performed at any time during the study as determined necessary by the investigator or required by local regulations.

Page: 66 of 86

Table 10-1: Protocol-Required Safety Laboratory Assessments

Laboratory Assessments	Parameters		
Hematology	Hemoglobin Hematocrit RBC count	WBC Count with Differential: Neutrophils Lymphocytes Monocytes Eosinophils Basophils	Platelet Count
Clinical chemistry ¹	BUN or Urea	Potassium	Aspartate Aminotransferase (AST) / Serum Glutamic- Oxaloacetic Transaminase (SGOT)
	Creatinine	Sodium	Alanine Aminotransferase (ALT)/ Serum Glutamic- Pyruvic Transaminase (SGPT) Alkaline Phosphatase (ALP)
	Glucose (non-fasting) ²	Calcium (Total Calcium)	Total protein Total and direct bilirubin Albumin
Other screening tests	Testosterone PSA		

NOTES:

Abbreviations: BUN blood urea nitrogen, PSA prostate specific antigen, RBC red blood cells, WBC white blood cells.

Investigators must document their review of each laboratory safety report.

¹ Details of liver chemistry stopping criteria and required actions and follow-up assessments after liver stopping or monitoring event are given in Section 7.1 and Section 6. All events of ALT ≥3 × upper limit of normal (ULN) and bilirubin ≥2 × ULN (>35% direct bilirubin) or ALT ≥3 × ULN and international normalized ratio (INR) >1.5, if INR measured, may indicate severe liver injury (possible Hy's Law) and must be reported as an SAE (excluding studies of hepatic impairment or cirrhosis).

² In case of fasting glucose is required, Daro should be taken after blood drawn with food as recommended.

Page: 67 of 86

10.3 Appendix 3: Adverse Events: Definitions and Procedures for Recording, Evaluating, Follow-up, and Reporting

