Results from the ARAMIS study led to the Food and Drug Administration (FDA), European Medicine Agency (EMA) and other regulatory authorities' approval of darolutamide for the treatment of men with nmCRPC.

Darolutamide is also being investigated in the metastatic hormone-sensitive prostate cancer. ARASENS is a randomized phase 3 study assessing the combination of ADT and docetaxel with or without darolutamide in mHSPC that has completed enrollment (Smith et al. 2022). ARANOTE is an ongoing study comparing the efficacy and safety of darolutamide and ADT versus ADT alone in mHSPC (Haresh et al. 2022).

Men in early stage of prostate cancer are concerned about the side-effects related to the ADT, therefore, optimizing treatment is of high importance to patients and caregivers. Drug induced adverse events may lead to a reduced quality of life, hence, treatments with favorable safety profiles could fulfill a medical need by providing an alternative to treatment with ADT.

Due to the fact that darolutamide is potent antiandrogen with strong efficacy and favorable safety and tolerability, there is rationale to study darolutamide in men with experiencing BCR prostate cancer. The available safety and efficacy data suggest that patients who participate in this trial are not placed at undue risk. Overall, the benefit/risk assessment for darolutamide monotherapy for hormone-naïve PC patients is favorable.

Cases of idiosyncratic drug-induced liver injury (DILI) with increases in ALT and/or AST to ≥ 5 and ≥ 20 x ULN, including with concomitant bilirubin elevation > 2x ULN, have been reported with darolutamide. Liver function tests abnormalities were reversible upon darolutamide discontinuation. Please see Section 6.2 and Section 7.1.

Page: 34 of 86

3. Objectives and Endpoints

Table 3-1: Lead-in Phase Objectives and Endpoints

Objectives	Endpoints
Primary	
To evaluate the impact of darolutamide monotherapy on serum testosterone level over a 12-week intervention period	Change in serum testosterone level from baseline to week 12
Secondary	
To evaluate the impact of darolutamide monotherapy on serum testosterone level over the course of a 52-week intervention period	Change in serum testosterone level from baseline at week 24 and 52
Assess PSA response rate	Serum PSA Week 4, 12, 24, 36, 52
To assess safety of darolutamide monotherapy in patients with hormone-naïve prostate Cancer with BCR	AE assessments using NCI CTCAE (v.5.0)

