Grade 2-3-4	If ALT or AST rise to >3 ULN: Per investigator's decision whether to reduce or interrupt the study intervention. Monitor LFT (ALT, AST, total and direct bilirubin, ALP) and INR within 72 hours after the onset and then as frequently as needed according to Investigator's clinical judgment, until ALT and/or AST returns to baseline or normal values.	If ALT or AST rise to >3 ULN: Participants must be discontinued from the study treatment in case of hepatic transaminase elevations suggestive of idiosyncratic DILI considered to be causally related to study intervention. DILI should be suspected after other causes of liver injury, have been excluded. Please see Section 10.3.5 for further guidance. Criteria for study treatment discontinuation (FDA 2009): • ALT or AST >8 x ULN • ALT or AST >5 x ULN for more than 2 weeks • ALT or AST >3 x ULN and (TBL >2 x ULN or INR >1.5) • ALT or AST >3 x ULN with the appearance of fatigue, nausea, vomiting, right upper quadrant pain or tenderness, fever, rash, and/or eosinophilia (>5%)
All grades Further recommendations	 If ALT and AST return to normal values or to baseline after study intervention interruption, study intervention may be restarted at the reduced dose of 300 mg bid If, at the reduced dose, there is no increase of ALT or AST in the subsequent two weeks, full dose may be resumed. If, at the reduced or full dose, ALT or AST values rise again, study intervention should be permanently discontinued. Monitor LFTs until ALT and/or AST return to baseline or normal values. 	

Abbreviation: AE, Adverse events; bid, Twice daily; NCI-CTCAE v 5.0, National cancer institute-Common terminology criteria for adverse events version 5.0; TEAE, Treatment emergent adverse event.

^a If there is no recovery after 28 consecutive days, treatment with study intervention should be permanently discontinued.

^b When AE returns to baseline or is resolved, re-escalation to 600 md bid may be considered by the investigator.

[°] If, following a re-escalation to 600 md bid a second Grade ≥3 study intervention TEAE occurs, a permanent dose reduction to 600 mg bid is required. A third occurrence of a Grade ≥3 study intervention related TEAE requires permanent discontinuation of treatment with study intervention.

Note: table excludes clinically non-significant and asymptomatic laboratory abnormalities.

Page: 47 of 86

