8.7.1 Time Period and Frequency for Collecting AE and SAE Information

All AEs will be collected from the signing of the ICF until the EOT visit or end of active follow up.

Medical occurrences that begin before obtaining informed consent will be recorded on the medical history section of the case report form (CRF). Information on major diseases that have occurred in the study subject that might affect function of critical organs (e.g., renal failure, hepatic insufficiency, heart disease) should be collected at screening. Collection of additional clinical history or data that is considered related or appropriate information for study

Page: 54 of 86

intervention/disease under study or deemed relevant by the investigator should also be included.

Medical occurrences that begin before the start of study treatment but after obtaining informed consent will be recorded on the AE section of the case report form (CRF).

Medical occurrences that started before but deteriorated after obtaining informed consent will be recorded as AEs.

All SAEs will be recorded and reported to the Sponsor or designee within 24 hours if investigator awareness, as indicated in Appendix 3. The investigator will submit any updated SAE data to the Sponsor within 24 hours of it being available.

Investigators are not obligated to actively seek AE or SAE in former study participants. However, if the investigator learns of any SAE, including a death, at any time after a participant has been discharged from the study, and he considers the event to be reasonably related to the study treatment or study participation, the investigator must promptly notify the Sponsor.

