8.7.4 Regulatory Reporting Requirements for SAEs

Prompt notification by the investigator to the Sponsor of a SAE is essential so that legal obligations and ethical responsibilities towards the safety of participants and the safety of a study treatment under clinical investigation are met.

The Sponsor has a legal responsibility to notify both the local regulatory authority and other regulatory agencies about the safety of a study treatment under clinical investigation. The Sponsor will comply with country-specific regulatory requirements relating to safety reporting to the regulatory authority, Institutional Review Boards (IRB)/Independent Ethics Committees (IEC), and investigators.

Investigator safety reports must be prepared for suspected unexpected serious adverse reactions (SUSAR) according to local regulatory requirements and Sponsor policy and forwarded to investigators, as necessary.

Page: 55 of 86

An investigator who receives an investigator safety report describing a SAE or other specific safety information (e.g., summary or listing of SAEs) from the Sponsor will review and then file it along with the Investigator's Brochure and will notify the IRB/IEC, if appropriate, according to local requirements.

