10.3.2 Definition of SAE

If an event is not an AE per definition above, then it cannot be an SAE even if serious conditions are met (e.g., hospitalization for signs/symptoms of the disease under study, death due to progression of disease).

An SAE is defined as any untoward medical occurrence that, at any dose:

Results in death

Is life-threatening

The term 'life-threatening' in the definition of 'serious' refers to an event in which the participant was at risk of death at the time of the event. It does not refer to an event, which hypothetically might have caused death, if it were more severe.

Requires inpatient hospitalization or prolongation of existing hospitalization

In general, hospitalization signifies that the participant has been detained (usually involving at least an overnight stay) at the hospital or emergency ward for observation and/or treatment that would not have been appropriate in the physician's office or outpatient setting. Complications that occur during hospitalization are AEs. If a complication prolongs hospitalization or fulfills any other serious criteria, the event is serious. When in doubt as to whether "hospitalization" occurred or was necessary, the AE should be considered serious.

Hospitalization for elective treatment of a pre-existing condition that did not worsen from baseline is not considered an AE.

Results in persistent disability/incapacity

- 1. The term disability means a substantial disruption of a person's ability to conduct normal life functions.
- 2. This definition is not intended to include experiences of relatively minor medical significance such as uncomplicated headache, nausea, vomiting, diarrhea, influenza, and accidental trauma (e.g., sprained ankle) which may interfere with or prevent everyday life functions but do not constitute a substantial disruption.

Page: 69 of 86

Is a congenital anomaly/birth defect

Other situations:

- 1. Medical or scientific judgment should be exercised in deciding whether SAE reporting is appropriate in other situations such as important medical events that may not be immediately life-threatening or result in death or hospitalization but may jeopardize the participant or may require medical or surgical intervention to prevent one of the other outcomes listed in the above definition. These events should usually be considered serious.

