4.5.2 Adverse Events

Treatment-emergent AE (TEAE) is defined as any event arising or worsening after the first dose of study drug until 30 days after the last dose of study drug.

An overview of TEAEs will be summarized for the appropriate safety analysis set at the three data cuts. The following summaries will be done.

- Overview of TEAEs
- TEAEs by MedDRA ad worst CTCAE grade
- TEAEs by MedDRA ad worst CTCAE grade 3, 4 or 5
- TEAEs: number of subjects by primary SOC and PT
- TEAEs leading to permanent discontinuation of study drug: number of subjects by primary SOC and PT
- Number of subjects with TEAE by PT in decreasing order
- Drug-related TEAEs: number of subjects by primary SOC and PT

• Drug-related TEAEs leading to permanent discontinuation of study drug: number of subjects by primary SOC and PT

Page: 18 of 31

- Number of subjects with drug-related TEAE by PT in decreasing order
- SAEs: number of subjects by primary SOC and PT
- TESAEs: number of subjects by primary SOC and PT
- Drug-related TESAEs: number of subjects by primary SOC and PT
- TE non-SAEs (excluding TESAEs): number of subjects by primary SOC and PT

Additionally, feminizing side effects as described in Section 4.3, will be summarized by

- Overview of TEAEs of feminizing side effects
- Number of subjects with TEAEs of feminizing side effects by PT in decreasing order
- Treatment-emergent study drug-related adverse events of feminizing side effects by MedDRA SOC and PT and worst CTCAE grade
- Number of subjects with TEAEs of feminizing side effects leading to permanent discontinuation of study drug by PT in decreasing order
- Number of subjects with drug-related TEAEs of feminizing side effects by PT in decreasing order
- Number of subjects with drug-related TEAEs of feminizing side effects leading to permanent discontinuation of study drug by PT in decreasing order
- SAEs of feminizing side effects: number of subjects by primary SOC and PT
- TESAEs of feminizing side effects: number of subjects by primary SOC and PT
- Drug-related TESAEs of feminizing side effects: number of subjects by primary SOC and PT

AEs of special topics will be summarized by

• Number of subjects with special topics for adverse events

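### The automatic SAE rule for possible severe liver injury (Protocol Table 10-1, note 1) counts ALT only, while the matching discontinuation criterion in Table 6-1 counts ALT or AST

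*Protocol*

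**What the plan says.** Protocol Section 10.2, Table 10-1, note 1 defines when a liver laboratory finding has to be reported as an SAE. The first limb reads "All events of ALT ≥3 × upper limit of normal (ULN) and bilirubin ≥2 × ULN (>35% direct bilirubin"). The second is ALT at the same level with INR above 1.5, where INR was measured. The note calls these possible Hy's Law cases. It also links itself to the stopping rules: "Details of liver chemistry stopping criteria and required actions and follow-up assessments after liver stopping or monitoring event are given in Section 7.1". It cites Section 6 for them too.

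Section 6.2.2.1, Table 6-1 lists criteria for discontinuing study treatment. One of them is "ALT or AST >3 x ULN and (TBL >2 x ULN or INR >1.5").

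Section 2.3 describes reported cases of idiosyncratic liver injury on darolutamide "with increases in ALT and/or AST to ≥ 5 and ≥ 20 x ULN, including with concomitant bilirubin elevation > 2x ULN", and Section 6.2.2.1 repeats this.

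Seriousness has consequences elsewhere. Section 8.7.1 says "All SAEs will be recorded and reported to the Sponsor or designee within 24 hours" of investigator awareness. SAP Section 4.5.2 plans separate SAE tables, including "TESAEs: number of subjects by primary SOC and PT".

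**The concern.** Note 1 takes one laboratory picture out of the investigator's discretion and makes it serious by rule. It does so for ALT-led cases only. Elsewhere the protocol treats the two enzymes alike: both are limited at entry (Section 5.1, criterion 9d), both are required tests, both trigger monitoring and discontinuation in Table 6-1, and both appear in the description of the known risk. No reason is given for leaving AST out of the SAE rule, and no other section extends the rule to AST.

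What is at stake is consistent classification. For an AST-led rise with the same bilirubin or INR finding, the 24-hour report and entry in the SAE and TESAE tables depend on the general definition in Section 10.3.2: "Medical or scientific judgment should be exercised in deciding whether SAE reporting is appropriate in other situations such as important medical events". Two sites could classify the same results differently.

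**Working it through.** No figure in the plan needs reproducing, so the check sets the two rules side by side and applies them to example values.

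| Element | Table 10-1, note 1 (SAE) | Table 6-1 (discontinuation) |
|---|---|---|
| Transaminase | ALT ≥3 x ULN | ALT or AST >3 x ULN |
| Bilirubin limb | ≥2 x ULN, >35% direct | total >2 x ULN |
| INR limb | >1.5, if measured | >1.5 |
| Drug | not drug-specific | written mainly for darolutamide (Section 6.2.2.1, reductions to 300 mg bid) |
| Condition | none on causality | same cell refers to suspected DILI judged causally related |

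The patterns are close but not identical. Apart from the choice of enzyme, the laboratory differences are the strictness of the inequalities, the direct-bilirubin condition and the remark on whether INR was measured.

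The rules as logical conditions, with enzymes and bilirubin in multiples of ULN:

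- Table 6-1 criterion: (ALT >3 or AST >3) and (TBL >2 or INR >1.5).
- SAE rule now: (ALT ≥3 and TBL ≥2 and direct >35%) or (ALT ≥3 and INR >1.5).
- SAE rule with the change: the same, with (ALT ≥3 or AST ≥3) in each limb.

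Applied to illustrative values:

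| Case | Table 6-1 criterion | SAE rule now | SAE rule changed |
|---|---|---|---|
| ALT 4, AST 2, INR 1.8 | met | met | met |
| AST 4, ALT 2, INR 1.8 | met | not met (ALT 2 <3) | met |
| ALT 4, AST 2, TBL 2.5, 50% direct | met | met | met |
| AST 4, ALT 2, TBL 2.5, 50% direct | met | not met (ALT 2 <3) | met |
| AST 4, ALT 2, TBL 2.5, 20% direct, normal INR | met | not met | not met (20% ≤35%) |

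Rows 1 and 2, and rows 3 and 4, differ only in which enzyme is raised, and the automatic SAE status changes with it. Row 5 stays outside because of the direct-bilirubin condition, which is a defensible restriction and is left alone.

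The data for an AST limb are already collected. AST and total and direct bilirubin are in Table 10-1. When either enzyme exceeds 3 x ULN, Table 6-1 asks for liver tests, including direct bilirubin, and INR within 72 hours.

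Number of participants under note 1: 25 in the lead-in, and 25 + 40 = 65 if the randomized phase opens (Section 1.4).

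**The case against.** The strongest reply is that stopping rules and seriousness rules need not match. Table 6-1 also lists ALT or AST >8 x ULN, >5 x ULN for more than two weeks, and >3 x ULN with symptoms. Note 1 makes none of these an automatic SAE, even when ALT is the raised enzyme. A stopping rule wider than the SAE rule is therefore the general pattern here. That stands, and the point does not rest on a requirement that the rules coincide. It rests on note 1 singling out the bilirubin/INR pattern as possible severe injury and then omitting, without explanation, an enzyme the protocol names in its own description of the risk.

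The second reply is that other routes catch the case. Section 10.3.2 says important medical events should by default be treated as serious. Section 10.3.5 requires prompt notice to the sponsor's medical representative when DILI is suspected, and Section 8 has immediate safety concerns discussed with the sponsor. Clinically relevant laboratory changes are recorded as AEs (Section 8.8.3). This also stands and limits the consequence. None of these routes is an automatic SAE classification, however.

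Three stronger readings are not supported:

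- A reader might infer that every such participant must stop treatment and yet goes unreported. The Table 6-1 cell ties discontinuation to suspected DILI judged causally related, so an AST-led case meets a listed criterion but does not certainly stop treatment. It also stays in the AE record.
- A reader might infer that SUSAR reports would be missed. Section 8.7.4 says "Investigator safety reports must be prepared for suspected unexpected serious adverse reactions (SUSAR"), and that status also requires unexpectedness. Liver injury with raised ALT and/or AST and bilirubin is already described for darolutamide. Whether a new case would be unexpected is not settled by the documents.
- A reader might infer that the sponsor would not hear of the case. The routes above make that unlikely.

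**Conclusion.** The mismatch is real and in current text. An AST-led case with raised bilirubin (>35% direct) or INR >1.5 is an SAE only if the investigator judges it an important medical event or another seriousness criterion applies. The ALT-led equivalent is an SAE by rule. What is affected is the 24-hour report and whether the case is counted in the SAE/TESAE tables or only among other TEAEs.

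Severity is minor, and this is best treated as a cheap improvement. Such cases are probably rare, but that is an assumption because the documents give no rate. The stopping rules, the primary and secondary testosterone analyses, the sample size and the power are unaffected. The conclusion assumes that note 1 is applied as written, with ALT not read to include AST.

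**What to change.** In Table 10-1, note 1, replace ALT by ALT or AST in both limbs, so that either enzyme at ≥3 x ULN, with bilirubin ≥2 x ULN (>35% direct) or with INR >1.5 if measured, has to be reported as an SAE. Leave the thresholds, the direct-bilirubin condition, Table 6-1, Section 10.3.5 and all stopping and causality wording as they are.

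The cost is two words added in two places in one footnote. No new test or visit is needed, and the SAP tables need no change. The downside is an occasional extra SAE report for an AST rise that proves to have another cause.
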